Additional studies are needed to further evaluate the possible benefits and potential limitations of CGM technology in the perioperative setting. We are interested in how CGM technology could improve glycemic management in the preoperative setting. We aim to evaluate utilization of CGM technology in the preoperative setting by enrolling a total of 220 subjects with diabetes mellitus. The original feasibility study included 20 subjects who all were wearing the Freestyle Libre Pro CGM device in an effort to determine the feasibility of wearing the device for up to 14 days prior to their scheduled surgery. No randomization was involved in that initial cohort. This expanded study will now randomize subjects to utilization of the Freestyle Libre Pro device versus Freestyle Libre 2 device. Subjects will be enrolled during the preoperative appointment and have a 50% chance of having a Freestyle Libre Pro CGM device vs Freestyle Libre 2 device placed during the preoperative appointment. Current standard of care with monitoring glycemic range utilizing point of care blood glucose fingersticks, serum glucose, as well as arterial glucose as indicated will be utilized for all subjects. Additionally, patients randomized to the Freestyle Libre 2 device will be instructed to scan the sensor every 8 hours at home.

Objectives

1-Investigate time in range during preoperative period prior to the day of surgery in patients wearing CGM;

2-Compare average glucose from holding room in patients wearing Freestyle Libre Pro CGM vs. patients wearing Freestyle Libre 2 CGM

- To evaluate use of CGM technology in the preoperative setting: evaluate feasibility of placement of CGM during preoperative clinic visit
- To assess how CGM technology could improve glycemic management in the perioperative setting

Methods and Measures

Design

- This is a prospective analysis of a cohort study of subjects with diabetes mellitus undergoing surgery.
- Prospectively, subjects will be undergoing surgery that does not involve the upper extremity given the potential need for CGM placement site.
- We will be analyzing data obtained from the Freestyle Libre Pro and Freestyle Libre 2, which will be placed on a randomized group (1:1) of consented subjects. 100 subjects will receive the Freestyle Libre Pro CGM and 100 subjects will receive the Freestyle Libre 2 CGM.
- Subjects will wear CGM throughout perioperative period.

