- CGM will be in use for up to 14 days (total preoperative + postoperative, or until discharge, whichever comes first).
- For the Freestyle Libre 2 CGM group, an endocrinologist will review the CGM data within a week of placement of CGM, and may recommend medication changes based on CGM data to the study subject.
- Regardless of the group, all subjects will receive standard of care during surgery and hospitalization with fingerstick blood glucose checks at Atrium Health Wake Forest Baptist. It is standard of care for fingerstick blood glucose checks to occur upon arrival to preoperative holding bay and upon arrival to Post Anesthesia Care Unit. Intraoperative

and postoperative glucose checks are at the discretion of the anesthesiologist while in the recovery area, and at the discretion of the surgical team when on the postoperative floor.

- CGM device will be removed by research team prior to discharge.

Setting

The study takes place at an academic medical center, Atrium Health Wake Forest Baptist in Winston- Salem, NC.

Subjects Selection Criteria

- **Inclusion Criteria**

- 18 years of age or older
- Diagnosed with diabetes mellitus
- Undergoing inpatient surgery at Atrium Health Wake Forest Baptist
- Smartphone compatible with the Freestyle Libre 2 CGM phone application

- **Exclusion Criteria**

- Undergoing surgery that would limit the placement of CGM to the posterior aspect of the upper extremity
- CGM devices do not pose a risk to mother or fetus, so pregnancy will not be an exclusion criteria.
- Undergoing cardiac surgery

- **Sample Size**

There will be a total of 220 subjects selected during preoperative evaluation appointment at Atrium Health Wake Forest Baptist. In order to get 220 evaluable subjects, a total of up to 240 subjects may be consented. This total of subjects includes the 20 pilot subjects that were previously enrolled under this protocol.

Interventions and Interactions

- Subjects will be identified at time of preoperative appointment at Atrium Health Wake Forest Baptist. Similar to our previous CGM study, the research team will review subjects scheduled for Preoperative Assessment Clinic visit for inclusion criteria and exclusion criteria. Subjects that meet criteria will be approached by research team during Preoperative Assessment Clinic visit in a private clinic room. This is a private clinic room with adequate space to discuss study participation.

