- Written informed consent will be obtained from individuals that meet above inclusion criteria by a member of the research team.
- Once consent has been obtained, the subjects will be randomized to receive either the Freestyle Libre Pro or Freestyle Libre 2. CGM will be placed on the subject prior to their discharge from their preoperative assessment clinic visit with contact information for research staff being given for any issues that may arise.
- Research staff will then meet the subject in the holding room on the morning of surgery to ensure device remains in place. The subject will then be followed during the perioperative period.
- Chart review will occur to collect data on the standard of care glucose values obtained from preoperative holding bay and post anesthesia care unit.
- The CGM device will be removed prior to discharge.
- Typical standard of care blood sugar collection occurs in preoperative holding bay (before subject is taken back to the OR) and upon arrival to the post anesthesia care unit (after surgery). Intraoperative blood sugar collection is at the discretion of the anesthesiologist.

- For all consented study subjects, we will retrospectively review the CGM data to compare to 1. The time of the preoperative blood sugar collection and 2. The time of the post anesthesia care unit blood sugar collection. We will retrospectively note insulin administration in this study.
- Data collection for each subject will include subject demographics, status of diabetes mellitus diagnosis, comorbid conditions, all blood glucose values during admission, all chemistry laboratory during admission, as well as data obtained from the Freestyle Libre Pro and Freestyle Libre 2 CGM that is worn throughout the perioperative and postoperative setting.

Outcome Measure(s)

- Proportion of subjects who present on day of surgery with CGM still in place and functioning
- Comparison utilizing Freestyle Libre 2 CGM in the perioperative setting for subjects with diabetes mellitus compared with Freestyle Libre Pro CGM with current standard of care utilizing point of care blood glucose fingerstick.
- Subject satisfaction with CGM
- Comparison of number of events of hyperglycemia (>180 mg/dL) on day of surgery (preoperative holding room and post anesthesia care unit) in subjects wearing Freestyle Libre Pro CGM vs. subjects wearing Freestyle Libre 2 CGM

Analytical Plan

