Results will be analyzed comparing glycemic data from point of care fingerstick blood glucose values as well as serum glucose values of patients wearing Freestyle Libre Pro CGM to patients wearing Freestyle Libre 2 CGM and will be assessed statistically. Other inferential statistical analysis will be conducted as appropriate.

Human Subjects Protection

Subject Recruitment Methods

Only those subjects who have diabetes mellitus and are undergoing inpatient surgery at Atrium Health Wake Forest Baptist will be recruited for this study. Subjects will be identified with the assistance of the Anesthesiology team on day of preoperative assessment prior to planned surgery.

Informed Consent

Signed informed consent will be obtained from each subject by the investigators listed above at time of admission to Atrium Health Wake Forest Baptist. Risks, benefits, and alternatives will be explained to each subject.

Confidentiality and Privacy

Confidentiality will be protected by collecting only information needed to assess study outcomes, minimizing to the fullest extent possible the collection of any information that could directly identify subjects, and maintaining all study information in a secure manner. To help ensure subject privacy and confidentiality, only a unique study identifier will appear on the data collection form. Any collected subject identifying information corresponding to the unique study identifier will be maintained on a linkage file, stored separately from the data. The linkage file will be kept secure, with access limited to designated study personnel. Following data collection, subject identifying information will be destroyed (3 years after closure of the study by file deletion), consistent with data validation and study design, producing an anonymous analytical data set. Data access will be limited to study staff. Data and records will be kept locked and secured, with any computer data password protected. No reference to any individual subject will appear in reports, presentations, or publications that may arise from the study.

Data and Safety Monitoring

The principal investigator will be responsible for the overall monitoring of the data and safety of study subjects. The principal investigator will be assisted by other members of the study staff.

Reporting of Unanticipated Problems, Adverse Events or Deviations

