Any unanticipated problems, serious and unexpected adverse events, deviations or protocol changes will be promptly reported by the principal investigator or designated member of the research team to the IRB and sponsor or appropriate government agency if appropriate.

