APPENDIX:

Timeline

1. Day 1: Preoperative Assessment Clinic visit.
 - a. The timing of this visit varies, but is often a few days to a week or so prior to day of surgery.
 - b. Potential subject will be identified by research team (like we did for our previous CGM study)
 - c. Consent by PI or clinical research staff
 - d. Device placement (CGM) by research team
 - e. Subject wearing Freestyle Libre 2 CGM will be given protocol to scan the sensor at least every 8 hours at home. Otherwise, subjects should follow their usual routine for their blood sugar management.
2. Day 2 – 13: Day of surgery
 - a. The timing of this varies, but is often a few days after PAC visit.
 - b. If the patient is wearing a Freestyle Libre 2 CGM, an endocrinologist will review the data remotely within a week of placement and may recommend medication changes prior to day of surgery.
 - c. Blood sugar obtained in preoperative holding room bay by preoperative nurse (this is our standard of care at Atrium Health Wake Forest Baptist, this will not need to be protocolized, preoperative nurse should follow their usual routine for a subject with diabetes).
 - d. Device checked by research team in preoperative holding room (that CGM is still in place and functional).
 - e. If subject is discharged to home, CGM will be removed in PACU by research team prior to discharge.
3. Up to day 14: Post operative day 1
 - a. If subject stays overnight, CGM will be removed in subject hospital room by research team prior to discharge.

References

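### Only the Libre 2 arm may receive CGM-driven medication recommendations before surgery, yet no by-arm measure of low glucose or other harm is planned

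*Combined protocol and SAP*

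**What the plan says.** **The difference between arms.** Under Design, the endocrinologist who reviews Libre 2 data "may recommend medication changes based on CGM data to the study subject". Item 2b of the Appendix Timeline places this before surgery: "an endocrinologist will review the data remotely within a week of placement and may recommend medication changes prior to day of surgery". No equivalent step is described for the Libre Pro arm.

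**What is counted.** The one event count under Outcome Measure(s) is "Comparison of number of events of hyperglycemia (>180 mg/dL) on day of surgery", taken in the holding room and the post anesthesia care unit.

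**What is collected.** The data list under Interventions and Interactions takes "all blood glucose values during admission, all chemistry laboratory during admission" from the chart. The same sentence goes on to include "data obtained from the Freestyle Libre Pro and Freestyle Libre 2 CGM that is worn throughout the perioperative and postoperative setting". Objective 1 uses the sensor data from the home interval: "Investigate time in range during preoperative period prior to the day of surgery in patients wearing CGM".

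**What is said about safety.** Under Data and Safety Monitoring, "The principal investigator will be responsible for the overall monitoring of the data and safety of study subjects", with help from study staff. The section on reporting of unanticipated problems, adverse events or deviations adds one rule: "Any unanticipated problems, serious and unexpected adverse events, deviations or protocol changes will be promptly reported by the principal investigator" or a delegate, to the IRB and, where appropriate, the sponsor or a government agency.

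**The concern.** A medication recommendation made to a subject at home is the active part of the Libre 2 arm. Its intended effect is better glucose control, and its natural counterpart is low glucose. The background text itself names prevention of hypoglycemia as a reason to use CGM and cites a perioperative target of 80-180 mg/dL, so both ends of the range matter to this trial.

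The plan measures one end. It compares average holding-room glucose (Objective 2) and counts values above 180 mg/dL. A lower average or fewer high values would be read in favour of Libre 2. Nothing planned would show whether that came with more lows, or with events at home after a changed regimen. At stake is a one-sided conclusion: a benefit that was measured, beside a harm that nobody was asked to look for.

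**Working it through.** The documents give no event rate, power figure or safety target, so there is no figure to reproduce. The check is to take each kind of harm that could occur between sensor placement and surgery and see which part of the plan would pick it up.

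| Event at home before surgery | Outcome list | Admission chart data | Sensor data | Reporting rule |
|---|---|---|---|---|
| Low glucose without symptoms | No | Outside window | Recorded, no summary planned | Only if judged an unanticipated problem |
| Low glucose with symptoms or needing help | No | Outside window | Glucose value only | Only if judged unanticipated, or both serious and unexpected |
| Unplanned emergency or hospital care for glucose | No | Outside window, reading admission as the surgical stay | Not shown | As above |
| Sensor-site reaction | No; only whether the sensor is in place and working | Outside window | Not shown | As above |

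No row reaches a planned count by arm.

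**Length of the interval.** The Timeline puts placement on Day 1 and surgery on Day 2 to Day 13. The home interval is therefore 2 - 1 = 1 day at the shortest and 13 - 1 = 12 days at the longest. The Timeline says that a gap of a few days is common, so the upper bound is not typical. It shows only that the interval exists and lies before the chart window.

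**Whether time in range fills the gap.** For any lower and upper limit, the three shares of sensor time add to 100%:

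time in range = 100% - time below range - time above range.

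So the difference between arms in time in range equals minus the sum of the differences in time below and time above. Libre 2 could show more time in range while time below range also rises, provided time above range falls by more. Time in range alone cannot separate the two, and the plan does not define the range.

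**Whether mean glucose fills the gap.** It does not. A lower mean can come from fewer highs, more lows, or both. The holding-room mean also describes the morning of surgery, not the days before it.

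**The case against.** The strongest reply is that the home interval is not without data. Both arms wear a sensor from the clinic visit, the data list includes the sensor data, and Objective 1 analyses the preoperative period. Low readings could be derived at any time. This stands, and it limits the point: what is missing is a planned count, not the glucose data. It does not remove the point, because a count chosen after the results are known carries less weight, and a trace cannot supply the other events.

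Second, the reporting rule governs what must be sent promptly; it does not forbid recording anything else. A reader might infer that it screens out expected harms. The text does not support that. The gap is an omission elsewhere in the plan, not a fault in that sentence.

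Third, a reader might infer that serious hypoglycemia at home would never be reportable because it is expected in diabetes. The documents do not define expectedness or list expected events, and the consent form, where risks might be set out, was not available for this review. Some such events might well be reported. The plan still does not say that they would be sought or compared between arms.

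Fourth, subjects receive a research contact, the principal investigator oversees safety, and staff check the sensor in the holding room. These are real safeguards, and the check would find a lost or failed sensor. However, the contact relies on the subject to call, the oversight text gives no event definition or schedule, and the sensor check concerns the device. The endocrinologist's review does look at Libre 2 traces, but in one arm only, and no further review after a medication change is described.

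**Conclusion.** The point holds as a gap in planned measurement. One arm may receive a treatment-changing recommendation before surgery. The plan has one event count for high glucose and none by arm for low glucose or adverse events. Followed as written, it could support a claim of better glucose with Libre 2 while being silent on the matching harm.

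No number can be put on the harm. The documents give neither an event rate nor the share of Libre 2 subjects who would receive a recommendation, and any rate spread over all 100 would only restate what was assumed. The conclusion does not depend on a rate: if no events appear in a report, that would not be a measured zero, because nobody was told to ask.

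It rests on two readings: that the chart window means the surgical admission, and that no separate safety-collection procedure exists outside these documents. If one does, the protocol should refer to it. The change should be made because answers not sought at the time may not be recoverable later.

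**What to change.** 1. **Outcome Measure(s).** Add low sensor glucose by randomised arm, from sensor placement to the day of surgery: time below a threshold, and number of events below it. Fix the threshold before analysis; the 80 mg/dL lower limit cited in the background is one candidate. This is an analysis cut-off, not a treatment rule. Use the CGM data already collected, and report the hours of usable sensor data in each arm. Since the arms wear different devices, say in the report that this comparison reflects the device as well as the care.
2. **Interventions and Interactions.** At the holding-room check and at sensor removal, ask every subject in both arms about serious hypoglycemia, unplanned emergency or hospital care for glucose, and sensor-site reactions since placement. Record the answers whether or not the event was expected, and tabulate them by randomised arm.
3. **Reporting section.** Keep the condition that an adverse event be serious and unexpected only as the trigger for prompt IRB reporting, and state that collection under item 2 is wider.

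The cost is protocol wording, a few questions at contacts that staff already make, and somewhere to record the answers. No new visit is needed. The questions will carry some recall error, emergency care elsewhere will rest on the subject's report, and the safety table may look less favourable than one built without asking.

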APPENDIX:

Timeline

1. Day 1: Preoperative Assessment Clinic visit.
 - a. The timing of this visit varies, but is often a few days to a week or so prior to day of surgery.
 - b. Potential subject will be identified by research team (like we did for our previous CGM study)
 - c. Consent by PI or clinical research staff
 - d. Device placement (CGM) by research team
 - e. Subject wearing Freestyle Libre 2 CGM will be given protocol to scan the sensor at least every 8 hours at home. Otherwise, subjects should follow their usual routine for their blood sugar management.
2. Day 2 – 13: Day of surgery
 - a. The timing of this varies, but is often a few days after PAC visit.
 - b. If the patient is wearing a Freestyle Libre 2 CGM, an endocrinologist will review the data remotely within a week of placement and may recommend medication changes prior to day of surgery.
 - c. Blood sugar obtained in preoperative holding room bay by preoperative nurse (this is our standard of care at Atrium Health Wake Forest Baptist, this will not need to be protocolized, preoperative nurse should follow their usual routine for a subject with diabetes).
 - d. Device checked by research team in preoperative holding room (that CGM is still in place and functional).
 - e. If subject is discharged to home, CGM will be removed in PACU by research team prior to discharge.
3. Up to day 14: Post operative day 1
 - a. If subject stays overnight, CGM will be removed in subject hospital room by research team prior to discharge.

References

